11.2 Virtual: Video Recordings

Video recordings will be used during virtual study visits in order to collect Talk Aloud data while the study subject completes the conjoint decision-making tool. Video recordings will be

made during a secure virtual visit by using the record function on Zoom to record the subject's feedback. All video recordings will be uploaded and stored by the research coordinator in a password protected file in Box.

12. RISKS/BENEFITS TO SUBJECTS

12.1 Potential Risk.

This is a minimal risk study. However, a participant may experience psychological stress while participating in the study. While this is unlikely to provoke significant problems, the PI ([name]) will be available for evaluation and referral to appropriate behavioral care if needed. Risks to privacy using telehealth and telecommunications are also potential concern. We recognize that while encryption of videoconferencing makes breeches of private information unlikely, not all risks to privacy can be completely eliminated. We will inform all participants using the telehealth equipment of this.

12.2 Protection Against Risks.

There is the risk of loss of confidentiality but this is minimal due to safeguards in place. All of the participant's information will be kept password protected and encrypted with access restricted to the Principal Investigator and designated senior staff.

12.3 Potential Benefits to the Subjects.

There may be no direct benefits to participating in this study. However, the study may help to assist older patients when making decisions about treatment options.

12.4 Alternatives to Participation.

Taking part in this study is voluntary. Participants are free not to take part or to withdraw at any time, for whatever reason without consequence.

13. COSTS FOR PARTICIPATION

There will not be any cost incurred to the participants during this study. Materials to complete the study procedures, such as an IPad, will be provided by the study team. These will be returned to the study team upon completion of the procedures.

14. PAYMENT FOR PARTICIPATION

Subjects will be given a \$30 gift card at the time of completion for their participation in the study to compensate for the time spent on study procedures.

15. DATA / SAMPLE STORAGE FOR FUTURE USE

15.1. All hardcopy research records will be stored onsite in the URMC, in locked research files at the WCI. The Cancer Center is secured with electronic key cards. Offices within the Cancer Center are again secured by key and data is kept in locked file cabinets. Electronic research records are stored on the URMC's password secured and firewall protected networks. These are the same methods of security used for patient medical records. All study data will be kept for a period of 7 years after the study and all reports and publications are complete.

15.3. All data collected for the current study will be used in post hoc analyses as appropriate. Data will not be used for future studies without prior consent of the patient. The patient's individual research record will not be shared with their treating physician, unless they provide consent or the patient's treating physician is a study physician, in which case they will have access to study data as a study co-investigator. Overall study results will be presented to participants, faculty and staff at the URMC after completion of the study. Study results will be presented at professional meetings and published.

15.4. The study coordinator will assign a numerical study ID to each participant once they have signed the consent form (chronologically based on the data they signed consent i.e., 001, 002, 003...). All study forms and questionnaires will use this number and the participant's first, middle, and last initials as identifiers, to ensure data integrity. Other identifying information will not exist on these forms. A complete list of study participants with study ID, name, and contact information will be maintained separately. This linkage information will only be accessible to the study coordinator, study investigators, and the individuals responsible for maintaining the database.

15.5. Additionally, data on the socio-demographics, clinical, and cancer and treatment characteristics will be collected and managed by the research teams at URMC using secure REDCap electronic data capture tools hosted at URMC. We will also evaluate the medical records for clinical characteristics and outcomes, and utilize REDCap to collect and manage this information.

16. DATA AND SAFETY MONITORING PLAN

Only adverse events (AEs) related to the study intervention or procedures will be reported. In other words, AEs related to cancer treatment will not be reported.

16.1. Adverse Event Reporting Requirements

16.1.1. Adverse events will be reported using the URCC Adverse Event form and/or as required by the Cancer Center Clinical Trials Office.

Adverse events will only be recorded for the time that the study subject is taking part in study procedures during their one time visit with the study coordinator.

16.1.2. Adverse events will be reported in accordance with the following guidelines:

	Grade 1	Grade 2			Grade 3				Grade 4		Grade 5	
		Unexpected		Expected	Unexpected		Expected		Unexpected	Expected	Unexpected	Expected
		with hospitalization	without hospitalization		with hospitalization	without hospitalization	with hospitalization	without hospitalization				
Unrelated	Not	Not	Not	Not	Not	Not	Not	Not	10 Calendar Days	Not	10 Calendar Days	10 Calendar Days
Unlikely	Required	Required	Required	Required	Required	Required	Required	Required	Required	Required	Required	Required
Possible	Not	Not	Not	Not	Not	Not	Not	Not	24-Hour; 5 Calendar Days	10 Calendar Days	24-Hour; 5 Calendar Days	10 Calendar Days
Probable	Required	10 Calendar Days	Required	Required	10 Calendar Days	10 Calendar Days	Required	Required	Required	Required	Required	Required
Definite												

Hospitalization is defined as initial hospitalization or prolongation of hospitalization for ≥ 24 hours, due to adverse event.

16.1.3. Adverse event reports will be submitted in one of the following ways:

(1) By email: (pdf)

(2) By mail:

(3) By fax:

16.1.4. An unexpected adverse event is defined as any adverse experience, the specificity or severity of which is not consistent with the risk information. This is a minimal risk study as detailed above.

16.1.5. A serious event refers to any event in which the outcome results in any of the following: death, a life-threatening adverse experience, inpatient hospitalization or prolongation of existing hospitalization, a persistent or significant disability, incapacity, or a congenital anomaly/birth defect. Important medical events that may not result in death, be life-threatening, or require hospitalization may be considered a serious adverse drug experience when, based upon appropriate medical judgment, they may jeopardize the participant and may require medical or surgical intervention to prevent one of the outcomes listed in this definition. We anticipate that any serious events will be related to standard of care cancer treatments and not due to the intervention. We will not collect adverse events related to cancer treatments.

16.1.6. Adverse events will be reported in accordance with institutional policies (University of Rochester, Research Subject Review Board, local IRB, URCC CCOP, CTO, and DSMB) as per their requirements.

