7.1.4. Duration

Participation in the study will last approximately 60-90 minutes during a one time in-person or virtual visit. If needed, our study team may follow up with the participant for further information for up to 2 months after the initial completion of the study procedures. After the study is completed, participant data will be maintained for 7 years at URMC and will be kept in a password-protected database.

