Figure 1 below is a representation of how the conjoint scenarios are displayed. This is an iterative process, whereby participants select one hypothetical scenario from the first set of options. They subsequently are presented with a second set of options and are asked to again select a preferred hypothetical scenario. Figure 1 is an image of how the scenarios appear to participants when using the online tool.

Figure 1:

Treatment 1	Treatment 2	Treatment 3
The treatment would:	The treatment would:	The treatment would:
		
Decrease my worry about the cancer	Decrease my worry about the cancer	Increase the number of years that I am likely to live
But the treatment may also cause me to:	But the treatment may also cause me to:	But the treatment may also cause me to:
		
Feel more tired and limit my day-to-day activities	Have changes in my thinking that limit my day-to-day abilities	Have changes in my thinking that limit my day-to-day abilities
and	and	and
		
Need more help from others for day-to-day activities	Be hospitalized due to side effects	Be hospitalized due to side effects
During the treatment my Quality of Life would be:	During the treatment my Quality of Life would be:	During the treatment my Quality of Life would be:
		
Relatively unchanged	Significantly worse than it is right now	Relatively unchanged
		

When participants have completed the exercise, the tool provides output ranking of the meta-attributes and three attributes (benefit of therapy, side effects of therapy, hardship). Figure 2 is an example image of how the output of patient preferences can appear for the meta-attribute and side effects of therapy.

Figure 2: Conjoint analysis output example of meta-attribute and attribute ranking.

As described below in study procedures, results of the conjoint analysis as well as geriatric assessment results are provided to participants. For oncologists, the results provided include the conjoint analysis output, geriatric assessment results, and CARG-BC score.

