7. GDS
8. GAD-7
9. OARS social functioning

Measures administered by the study coordinator will be completed first, then followed by the patient reported measures which will be completed as a component of the tool.

After completing the baseline GA measures, participants will then complete the DPT on the tablet provided by the study staff. Patients will be presented with several scenarios at once (similar to figure 1 above) and asked to select one that is consistent with their preferences. This process will repeat until all attributes are evaluated in the tool. While the subject is completing the DPT, they will be audio recorded in order to collect data for the Talk Aloud method.

After completing the GA and DPT, the summary of the results will be sent to the study email at [contact]. Once the results are emailed, the study coordinator will then show the participant their results on the IPad and will evaluate the patient's impression while they look over their results. We will ask participants to continue with the talk aloud method as they are reviewing the results provided by the conjoint analysis.

The summary of the results that contain a ranking of factors will be provided to the patient's oncologist and the participant will also be provided with their results either in the form of an email sent to their personal email address or in the form of a hard copy print out.

Once results have been provided to the patient, the study patient will then complete a quantitative measure (SUS) evaluating the usability of the tool (Table 2).

The SUS will be administered verbally and the coordinator will have the questions visually available on the IPad for the patient as we go over the questions with them. The study coordinator will record the patient's responses on a hard copy of the SUS form.

Lastly, we will ask additional questions to assess the usability of the tool at the end of the study.

1. Do you have any feedback about the tool?
2. What is your impression of the results in terms of format and understanding?
3. Do you feel that the results accurately reflect your preferences?

10.1.3 Virtual Visit:

The study coordinator will familiarize eligible patients to the study by using the following script when approaching for consent.

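### Adverse event recording stops when the single visit ends, so related distress that staff hear about at a permitted later contact cannot be recorded

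*Combined protocol and SAP*

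**What the plan says.** Section 16.1.1 limits recording by time: "Adverse events will only be recorded for the time that the study subject is taking part in study procedures during their one time visit". The opening paragraph of Section 16 limits reporting by cause. Events related to the intervention or its procedures are reported, those due to cancer treatment are not, and no time limit is given.

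Section 7.1.4 describes one visit and then allows later contact if needed: "our study team may follow up with the participant for further information for up to 2 months after the initial completion".

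On what participants receive, Section 9.4 says that "results of the conjoint analysis as well as geriatric assessment results are provided to participants". Sections 10.1.2 and 10.1.3 give them their results by email or as a printed copy. Before that, at an in-person visit, "the study coordinator will then show the participant their results on the IPad and will evaluate the patient's impression while they look over their results"; a virtual visit does the same by screen share.

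On risk, Section 12.1 says that "a participant may experience psychological stress while participating in the study" and that the principal investigator "will be available for evaluation and referral to appropriate behavioral care if needed". It adds: "Risks to privacy using telehealth and telecommunications are also potential concern". Section 12.2 says: "There is the risk of loss of confidentiality but this is minimal due to safeguards in place".

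Section 16.1.6 refers adverse event reporting to institutional policies. Section 16.2 provides for a spreadsheet of events and a yearly cumulative review by the Data Safety Monitoring Committee (DSMC).

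**The concern.** The visit is where the tool is used, but exposure to its output continues. The participant keeps the results. Under Section 9.4 these include geriatric assessment findings, and Table 1 shows that the assessment contains screens for depression, anxiety and cognition. A participant may reread them at home, and staff may speak to her weeks later.

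If she then reports distress that she attributes to the results, the word *only* in Section 16.1.1 leaves the coordinator no room to record it, however clear the relation to the study. The event is lost to the spreadsheet and to the DSMC's cumulative review. Any later statement about adverse events would then describe the visit alone, and a reader who saw only the relatedness rule in Section 16 would not know that.

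**Working it through.** The documents give no figure to reproduce here, so the check is a comparison of sections.

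1. **Scope by cause.** The opening of Section 16 includes events related to the intervention or procedures. It sets no end date.
2. **Scope by time.** Section 16.1.1 allows recording only during procedures at the one visit. An event must therefore pass both tests. Strictly, the first rule concerns reporting and the second recording, so the two can be applied together without contradiction. But an event that is not recorded cannot be reported, so the narrower rule decides.
3. **Does any section reopen the window?** Section 16.1.6 says which bodies' requirements govern reporting; it does not extend recording. Section 16.2 deals with events already in the system. Section 7.1.4 permits contact but attaches no adverse event enquiry to it. Section 12.1 offers evaluation and referral but no recording rule. None reopens the window.
4. **Can a related event fall outside it and still be known to staff?** Yes. The results are kept (Sections 9.4, 10.1.2 and 10.1.3) and contact is allowed for up to 2 months (Section 7.1.4). Take distress caused by the results and volunteered at such a contact:

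| Rule | Outcome for this event |
|---|---|
| Section 16, relation to the study | In scope |
| Section 16.1.1, time of event | Not recorded |
| Section 16.2, spreadsheet and cumulative review | Never reached |
| Section 12.1, evaluation and referral | Still available |

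5. **What is inside the window?** The first viewing of the results, with the coordinator watching and the talk-aloud continuing, then the SUS and the three feedback questions. A privacy breach during a Zoom visit also happens inside it.
6. **Scale.** The study plans 10 participants. Even with complete capture, no events in 10 would leave a one-sided 95% upper limit of 1 − 0.05^(1/10) = 0.259, about 26%, for the true event rate. The study could not establish safety under either window. The point concerns honest capture, not the precision of a rate.

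**The case against.** The strongest reply is that a visit-only window is a deliberate and proportionate choice for a single-visit usability study. Much of this stands:

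- The reaction most likely to matter, on first seeing the results, is observed at the visit.
- Care does not depend on the record, because the principal investigator's availability in Section 12.1 has no time limit.
- As far as the table in Section 16.1.2 can be read, Grade 1 events and many Grade 2 events need no expedited report, so ordinary upset would probably be logged and go no further.
- No objective concerns safety. Section 17 uses the qualitative data to improve the tool for a later trial and plans no safety claim.

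Three stronger readings are tempting, and the documents do not support them.

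- *A reader might infer that the plan names post-visit distress as a risk and then excludes it.* Section 12.1 names stress during participation. Distress at home is a reasonable extension, but it is not a named risk.
- *A reader might infer that every loss of confidentiality escapes the record.* A breach during the visit falls inside the window. Nor does any section class a breach as an adverse event; later breaches may be handled under the institutional policies cited in Sections 7.1.2 and 16.1.6, whose content is not given.
- *A reader might divide the visit length by the 2-month span and call the result the share of risk covered.* Contact is optional and is made to obtain information. It is not observed time at risk, and the chance of an event is not uniform across it.

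What the reply does not remove is that a related event already known to staff is excluded by a stated rule.

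**Conclusion.** The point holds in a limited form. Section 16.1.1 shuts out related events that staff may learn of at contacts the protocol itself permits, while the opening of Section 16 puts such events in scope by cause. The two should be aligned.

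The impact is low. The study is described as minimal risk, and the primary SUS result does not change. How many events would be affected cannot be estimated from the documents, since follow-up contact is made only if needed.

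The conclusion rests on two readings: that *only* in Section 16.1.1 is meant literally, and that the copy participants keep contains the geriatric assessment results that Section 9.4 says they receive. If the copy held the conjoint output alone, the gap would remain but matter less.

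**What to change.** Replace the timing sentence in Section 16.1.1 with wording such as:

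> Adverse events judged possibly, probably or definitely related to study procedures, or to receipt of the DPT or geriatric assessment results, will be recorded from consent until the last study contact that takes place, up to 2 months after the visit. Events related to cancer treatment will not be recorded.

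This uses attribution categories already in the Section 16.1.2 table and keeps the existing cancer-treatment exclusion. It adds no contacts. Capture after the visit stays passive, so the study report should say that later events were recorded only where a contact happened to take place.

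Privacy breaches after the visit can be left to the institutional policies; logging them as adverse events throughout the 7-year retention period is not warranted.

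The cost is a one-sentence amendment and perhaps a few more low-grade events to log among 10 participants.

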16.2. Data Safety Monitoring

16.2.1. All adverse events requiring reporting will be submitted to the current Project Coordinator as described in Section 11.1. Serious adverse event reports will be forwarded to the study chair and the Data Safety and Monitoring Committee (DSMC). Adverse events are entered into a protocol-specific spreadsheet.

16.2.2. Adverse event rates are monitored utilizing the spreadsheet. If a serious adverse event is reported frequently, the study chair will conduct a detailed review. The DSMC Committee Chair will be notified and will determine if further action is required.

16.2.3. The Data Safety Monitoring Committee (DSMC) will review study progress and cumulative reports of adverse events every year and as needed. An overall assessment of accrual and adverse events will enable the committee members to assess whether significant benefits or risks are occurring that would warrant study closure.

17. DATA ANALYSIS PLAN

Sawtooth software will be utilized for the conjoint analyses to determine prioritization of participant preferences [16, 17].

Usability testing is the evaluation of a program through the analysis of typical end user interactions, with iterative modifications [18]. The majority of usability problems can be identified in a small set of subjects (e.g. 8-10) [18].

Quantitative Analysis: The SUS ranges 0-100; a score >68 is above average [19]. Our goal will be to achieve a mean SUS score >68 amongst the 10 patients enrolled.

Qualitative Analysis: Audio-recordings capturing the “talk aloud” feedback will be transcribed and a Process Coding framework will be utilized to analyze the transcripts. Responses to the three feedback questions will also be transcribed and a Content Analysis framework will be utilized to analyze responses. Together, this qualitative data will be evaluated for themes to optimize usability of the tool for a planned subsequent RCT to evaluate the effect of the DPT on content of conversations between patients and their oncologists.

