1. PURPOSE OF STUDY

1.1. Overall Goal:

We have developed a Discussion Prioritization Tool (DPT) for older adults considering adjuvant chemotherapy. The DPT utilizes Conjoint Analysis (CA) methodology and the objective of the current study is to assess usability of this DPT in our target population, older adults with breast cancer and to adapt the tool to optimize usability for our target population.

1.2. Study objectives and Hypothesis:

1.2.1. Primary objective:

To evaluate the usability of the DPT in ten older adults considering adjuvant chemotherapy or has made a decision about receiving adjuvant chemotherapy for breast cancer within the past 12 months.

1.2.2. Secondary objective:

To adapt the DPT using “talk aloud” method to optimize usability for our target population.

1.2.3. Hypothesis:

The DPT tool will demonstrate adequate usability in older adults considering adjuvant chemotherapy or has made a decision about receiving adjuvant chemotherapy for breast cancer within the past 12 months.

1.2.4 Usability and feasibility metrics:

The usability and feasibility of the DPT will be evaluated based on the following:

Primary Usability Assessment Measures: System Usability Scale (SUS) (score on 10-item scale, total score ranging 0-100; higher score corresponds to greater usability). We will deem the tool usable if our mean SUS score among the 10 patients enrolled is >68.

Secondary Usability Assessment Measures:

- a) Recruitment rates (percentage of patients who are approached and agree to enroll)
- b) Talk Aloud Method (recordings of patients feedback while using the DPT)

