5. SUBJECT POPULATION

5.1 Subject Population:

The eligibility criteria is aimed at identifying older patients diagnosed with localized breast cancer who are being considered for adjuvant chemotherapy or has made a decision about receiving adjuvant chemotherapy for breast cancer within the past 12 months. Since our study team is developing a tool that incorporates geriatric specific factors, we will recruit patients who are aged 65 or older. The study will have no restrictions on race or gender. However due to the disease, we anticipate that most, if not all participants will be female.

5.2 Number of subjects:

Our study team expects 10 subjects to participate in the study. The majority of usability studies demonstrate that usability can be optimized in a small number of subjects (e.g. 10). We anticipate being able to enroll the targeted number of patients in <1 year duration.

5.3 Vulnerable Subjects:

Recruitment will exclude vulnerable populations such as fetuses, neonates, children, pregnant woman, prisoners, adults with decisional impairment, and institutionalized individuals.

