Comorbidity	
 • OARS Comorbidity 
 ○ A self-report of any existing comorbidities and their effect on the patient's daily life. • Polypharmacy 
 ○ We will record all prescription and non-prescription medications, dosage and frequencies from the medical records. Polypharmacy is defined as the use of 5 or more medications.
Psychological	
 • GDS 
 ○ A screening tool for depression • GAD-7 
 ○ A screening tool for anxiety
Social Functioning	
 • OARS Medical Social Support 
 ○ A survey that asks about the people involved in the patient's medical and social support.
1.c Coordinator Administered Assessments	
Cognition	
 • Mini-Cog (in person) 
 ○ An assessment consisting of memory questions and a drawing to help determine the current cognitive status of the patient. • Blessed (virtual) 
 ○ A 6 question assessment to help determine the current cognitive status of the patient.
Nutrition	
 • Nutritional Status 
 ○ Nutritional status of the patient will be determined by their current height, current weight, and weight 6mo. ago.

19.1 Table 2. System Usability Form (SUS).

System Usability Scale

Instructions: For each of the following statements, mark one box that best describes your reactions to the technology tool today.

	Strongly Disagree	2	3	4	Strongly Agree
1. I think that I would like to use this technology tool frequently.					
2. I found this technology tool unnecessarily complex.					
3. I thought this technology tool was easy to use.					
4. I think that I would need assistance to be able to use this technology tool.					
5. I found the various functions in this technology tool were well integrated.					
6. I thought there was too much inconsistency in this technology tool.					
7. I would imagine that most people would learn to use this technology tool very quickly.					

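### Does the single mean-SUS verdict fail because the plan never says the tool is held fixed for all 10 patients?

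*Combined protocol and SAP*

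**What the plan says.** Section 1.2.4 sets the only numerical success rule: "We will deem the tool usable if our mean SUS score among the 10 patients enrolled is >68". Section 17 restates it: "Our goal will be to achieve a mean SUS score >68 amongst the 10 patients enrolled". Both refer to one mean, 10 patients and one tool. The plan states no standard deviation, significance level, power or interval.

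Four places speak of changing or improving the tool:

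- Section 1.1 gives the objective as "to assess usability of this DPT in our target population, older adults with breast cancer and to adapt the tool to optimize usability".
- Section 1.2.2 aims to adapt the DPT with the talk-aloud "method to optimize usability for our target population".
- Section 17 cites a definition: "Usability testing is the evaluation of a program through the analysis of typical end user interactions, with iterative modifications".
- Section 5.2 supports the sample size with "The majority of usability studies demonstrate that usability can be optimized in a small number of subjects (e.g. 10").

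Three places bear on timing or version:

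- Section 17 ends by saying that the themes from the qualitative data will serve "to optimize usability of the tool for a planned subsequent RCT".
- Section 4.1 describes a single-arm pilot without cohorts or rounds. Section 10 gives one sequence of steps, varied only between in-person and virtual visits.
- The SUS form in section 19.1 (Table 2) asks the patient to "mark one box that best describes your reactions to the technology tool today" and has no field for a tool version.

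No section states that the DPT is locked during accrual.

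**The concern.** A study that both scores a tool and sets out to change it must be clear about what was scored. The feedback that would prompt changes arises at every visit, and section 5.2 allows up to a year for accrual, so a revision between patients would be practicable. Section 17 itself mentions iteration close to the success rule.

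Two things would be at stake. If the tool changed during accrual, the mean of 10 scores would average over versions and might describe none of them. It could pass a final version that scores below 68 or fail one that scores above it. If the tool changed only after the tenth patient, the mean would be valid for the version tested, but a reader might carry the word usable over to an adapted version with no SUS data. The rule is the study's only quantitative criterion, so its meaning matters.

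**Working it through.** **1. The plan's own figure.** The rule is mean SUS >68 with n = 10. With no standard deviation, error rate or power stated, there is no calculation to reproduce. The sample size rests on usability-testing convention.

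**2. Which reading does the text support?**

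| Text | Kind of statement | Bearing on timing |
|---|---|---|
| Section 17, definition mentioning iteration | General, referenced | None for this study |
| Section 5.2, optimising in small samples | General, about other usability studies | None for this study |
| Section 17, next sentence: most problems can be found in about 8 to 10 subjects | General | Supports n = 10 by detecting problems, not by revising between patients |
| Section 10.1, purpose of the talk-aloud method | Study-specific | Finding problems as the tool is used |
| Sections 1.1 and 1.2.2, adaptation as an aim | Study-specific | Met equally by adapting after patient 10 |
| Sections 4.1 and 10, one tool and one sequence of steps | Study-specific | No revision rounds |
| Section 17, use of the themes | Study-specific | Points to the later trial |

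The iterative process described with Figure 1 in section 9 is the run of choice sets shown to a patient, not revision of the tool. Every study-specific statement is compatible with a fixed tool, and the last two favour it.

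**3. Size under each reading.** Suppose k patients use a first version with mean m1 and 10 − k use a later one with mean m2, and let d = m2 − m1. Then

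pooled mean = (k × m1 + (10 − k) × m2)/10, and pooled mean − m2 = −k × d/10.

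- *Fixed tool:* d = 0, so the difference is 0.
- *One change after patient 5 (assumed):* the absolute difference is 5 × 5/10 = 2.5, 5 × 10/10 = 5.0 or 5 × 18/10 = 9.0 points for d = 5, 10 or 18.
- *Verdict reversed (assumed means, k = 5):* 65 then 70 gives (325 + 350)/10 = 67.5, and 72 then 67 gives (360 + 335)/10 = 69.5. Each lies on the other side of 68 from the later version.
- *Verdict unchanged (assumed means, k = 5):* 62 then 75 gives (310 + 375)/10 = 68.5, and 60 then 78 gives (300 + 390)/10 = 69.0. Both agree with the later version.

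So a reversal is possible under some assumed values and absent under others. The documents supply none of them.

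**4. Would a by-version analysis help?** The 95% half-width is t(0.975, n − 1) × SD/√n. For an assumed SD of 15:

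- n = 10: 2.262 × 15/√10 = 10.7 points.
- n = 5: 2.776 × 15/√5 = 18.6 points.
- n = 2 (a change after patient 8): 12.706 × 15/√2 = about 135 points, on a scale of 0 to 100.
- Difference between two versions with 5 patients each: 2.306 × 15 × √(2/5) = 21.9 points.

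Splitting 10 patients could not show whether a revision helped.

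**The case for a change.** The strongest case for acting is that a plausible reading is not a stated rule. No section locks the tool, and adaptation is an objective of this study, not only of the next one. A version field costs almost nothing. Section 8.1 registers the baseline visit date, but no change log is described that would link dates to versions, so an unrecorded version might not be recoverable later. Even with a fixed tool, the version taken into the later trial would be the adapted one, which has no SUS score.

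Part of this stands. The plan is silent on a freeze, and nothing in the removed or missing text appears to explain that. Recording any change to the tool is ordinary good practice. But a version field matters only if there are versions, and the plan describes none. The form's reference to the tool used that day ties each rating to what that patient saw, which is unambiguous. The point about the adapted version guards against a claim the plan does not make: sections 1.2.4 and 17 draw the conclusion from these 10 patients and do not extend it. Any formative pilot carries that risk of over-reading, and it is met in the wording of the report.

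**Conclusion.** The concern identifies a real silence but not a fault in the analysis. Read as its procedures are written, the plan tests one tool in 10 patients and adapts it afterwards. The mean-SUS rule then gives a sound verdict on the version tested, with zero distortion from pooling. The shift of k × d/10 points arises only if the tool is revised during accrual, which the documents do not establish, and every value used to size it is assumed.

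Adding detail would gain little. The 10-patient mean would remain the primary summary under either reading, and by-version estimates would be too imprecise to guide anyone. There is no hypothesis test, group comparison or treatment decision that depends on the result. An analyst would naturally report the score as belonging to the version the patients used, and would note a revision if one occurred. The conclusion rests on the fixed-tool reading. If the tool were in fact changed between patients, the pooled mean should not be taken as evidence about the final version alone.
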